4.3.2. Main analytical approach

Two one-sided equivalence tests will be applied to the ratios of each of C_{max} , $AUC(0-t)$, and $AUC(0-\infty)$ using the MUPFP as the test sample and the SDP as the reference. Test limits of the ratios to establish bioequivalence are 0.8 and 1.25.

PK parameters will be evaluated to estimate the relative bioavailability. Log-transformed C_{max} , $AUC(0-t)$, and $AUC(0-\infty)$ will be evaluated in a linear mixed-effects model with fixed effects for treatment, sequence, period, and a random effect for subject within sequence. The treatment differences will be back-transformed to present the ratios of geometric means between MUPFP and SDP treatments and the corresponding 90% CI.

$AUC(0-t_{last})$, $AUC(0-\infty)$, and C_{max} will also be analyzed using a linear fixed-effects model. This analysis will be performed using PK completer data set. The parameter estimates will be log-transformed before analysis. The model will include fixed effects for sequence, period, treatment, and subject nested within sequence. The LSmeans for each treatment, the difference in means between treatments, and the 90% CIs will be estimated from the model and back-transformed from the log scale to provide estimates of the geometric LSmeans, the ratio of the geometric LSmeans, and the 90% CIs. This method is consistent with the EMA recommended methodology of analysis.

4.4. Secondary Endpoint(s)/Estimands(s)] Analysis

The t_{max} will be analyzed through non-parametric methods. The median for each treatment and median of differences between the MUPFP and SDP treatments will be presented, along with the approximate 90% CI for the difference (see Hauschke). The p-value from a Wilcoxon ranked sum test will also be presented.

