### **9.3.3. Secondary Endpoints Analysis**

The  $t_{max}$  will be analyzed using Wilcoxon ranked sum test. Estimates of the median difference and 90% CIs will be calculated.

Additional PK analyses may be conducted if deemed appropriate.

All IP, study device, and protocol procedure AEs, and study device deficiencies/complaints will be listed, and if the frequency of events allows, data will be summarized using descriptive methodology.

The incidence of symptoms for each treatment will be presented by severity. Symptoms reported to occur prior to enrollment will be distinguished from those reported as new or increased in severity during the study. Each symptom will be classified by the most suitable term from the Medical Dictionary for Regulatory Authorities.

The number of IP-related SAEs will be reported.

If available, any incidence of erythema, induration, pain, pruritus, edema, bleeding, and bruising from injection site assessment will be listed.

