1.2. Study Design

[figure not shown]
This is a multicenter, open-label, randomized, 2-period, 2-sequence, crossover study conducted in healthy participants.

The study will include 2 treatment arms. Approximately 65 participants may be enrolled so that at least 54 participants complete the study. Participants will be randomly assigned 1:1 to the 2 treatment sequences. It is intended that approximately the same number of participants will be randomly assigned into each treatment sequence. The treatment sequence is:

- a single dose of 5 mg tirzepatide administered SC via MUPFP followed by SDP; or
- a single dose of 5 mg tirzepatide administered SC via SDP followed by MUPFP.

The study duration for individual participants, inclusive of screening, is expected to be approximately 14 weeks.

Following is the study design:

2. Statistical Hypotheses

The primary objective of this study is to evaluate bioequivalence of the MUPFP (test) and the SDP (reference) with a 5-mg dose, as assessed using tirzepatide PK parameters C_{max} , $AUC(0-t_{last})$, and $AUC(0-\infty)$ in healthy participants.

3. Analysis Sets

The following analysis sets are defined:

Table 2 Analysis sets

Participant Analysis Set / Population	Description
Enrolled	All randomly assigned participants.
Safety analysis set	All participants who are exposed to study intervention. Participants will be analyzed according to the intervention they actually received.
PK analysis set	All randomly assigned participants who received at least 1 study intervention and have evaluable PK data.
PK completer data set	For each PK primary parameter, only include participants who received all study interventions, and have evaluable PK data for both treatment periods.

4. Statistical Analyses

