4.1. General Considerations

Statistical analysis of this study will be the responsibility of Eli Lilly and Company or its designee.

PK analyses will be conducted for the PK analysis set according to the actual tirzepatide formulation received. Safety analyses will be conducted with the safety analysis set.

Summary statistics and statistical analysis will only be presented for data where detailed in this SAP. For continuous data, summary statistics will include the arithmetic mean, arithmetic standard deviation (SD), median, min, max and N; for log-normal data (eg, the PK parameters: area under the concentration versus time curve [AUCs] and maximum observed drug concentration [C_{max}]) the geometric mean and geometric coefficient of variation (CV%) will also be presented. For categorical data, frequency count and percentages will be presented. Data listings will be provided for all subjects up to the point of withdrawal. Summary statistics and statistical analyses will generally only be performed for subjects included in the relevant analysis population. For the calculation of summary statistics and statistical analysis, unrounded data will be used.

Mean change from baseline is the mean of all individual subjects' change from baseline values. Each individual change from baseline will be calculated by subtracting the individual subject's baseline value from the value at the timepoint. The individual subject's change from baseline values will be used to calculate the mean change from baseline using a SAS procedure such as Proc Univariate.

Data analysis will be performed using SAS[®] Version 9.4 or greater.

Additional exploratory analyses of the data will be conducted as deemed appropriate. Study results may be pooled with the results of other studies for safety and population PK analysis purposes

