4.3. Primary Analysis

4.3.1. Pharmacokinetic analysis

Pharmacokinetic parameter estimates will be determined using non-compartmental procedures in validated software program (Phoenix WinNonlin Version 8.1 or later).

Plasma concentrations of tirzepatide (LY3298176) will be used to determine the following PK parameters, when possible:

Parameter	Units	Definition
AUC(0-t _{last})	ng.h/mL	area under the concentration versus time curve from time zero to time t, where t is the last timepoint with a measurable concentration
AUC(0-∞)	ng.h/mL	area under the concentration versus time curve from time zero to infinity
%AUC(t _{last} -∞)	%	percentage of AUC (0-∞) extrapolated
C _{max}	ng/mL	maximum observed drug concentration
t _{max}	h	time of maximum observed drug concentration
t _{1/2}	h	half-life associated with the terminal rate constant (λ_z) in non-compartmental analysis
CL/F	L/h	apparent total body clearance of drug calculated after extra-vascular administration
V _z /F	L	apparent volume of distribution during the terminal phase after extra-vascular administration

Additional PK parameters may be calculated, as appropriate.

The software and version used for the final analyses will be specified in the clinical study report. Any exceptions or special handling of data will be clearly documented within the final study report.

Formatting of tables, figures and abbreviations will follow the Eli Lilly Global PK/PD/TS Tool: NON-COMPARTMENTAL PHARMACOKINETIC STYLE GUIDE. The version of the tool effective at the time of PK analysis will be followed.

General PK Parameter Rules

- Actual sampling times will be used in the final analyses of individual PK parameters, except for non-bolus pre-dose sampling times which will be set to zero.
- C_{max} and t_{max} will be reported from observed values. If C_{max} occurs at more than one timepoint, t_{max} will be assigned to the first occurrence of C_{max}.
- AUC parameters will be calculated using a combination of the linear and logarithmic trapezoidal methods (linear-log trapezoidal rule). The linear trapezoidal method will be applied up to t_{max} and then the logarithmic trapezoidal method will be used after t_{max}. The minimum requirement for the calculation of AUC will be the inclusion of at least three consecutive concentrations above the lower limit of quantification (LLOQ), with at least one of these concentrations following C_{max}.

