4.7. Changes to Protocol-Planned Analyses

There are no changes from the protocol specified statistical analyses.

5. Sample Size Determination

Approximately 65 participants may be enrolled so that approximately 54 evaluable participants complete the study. A sample size of 54 participants will provide at least 95% power that the 90% confidence interval of the geometric mean ratio of C_{max} and AUC between the 2 devices will fall within the equivalence range of 0.8 to 1.25. This assumes a nominal expected mean ratio of 1.05 (test vs reference), a within-subject coefficient of variation of 24%.

6. Supporting Documentation

Not applicable.

7. References

Signature Page for VV-CLIN-075821 v1.0

Approval

PPD

08-Mar-2023 13:35:51 GMT+0000

Signature Page for VV-CLIN-075821 v1.0

Approved on 08 Mar 2023 GMT

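### Does leaving the form of the tmax rank-sum test unstated in SAP 4.4 put the result at risk?

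*SAP*

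**What the plan says.** tmax is the only secondary PK endpoint (SAP 1.1). Protocol 9.3.3 says that it "will be analyzed using Wilcoxon ranked sum test", with a median difference and 90% CIs. SAP 4.4 says non-parametric methods will be used. The median for each treatment and the "median of differences between the MUPFP and SDP treatments will be presented", with an approximate 90% CI that carries a citation to a distribution-free bioequivalence procedure. The p-value sentence follows: "The p-value from a Wilcoxon ranked sum test will also be presented". The citation is attached to the interval, not to that sentence.

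Four other places bear on the reading:

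- SAP 4.1: "PK analyses will be conducted for the PK analysis set according to the actual tirzepatide formulation received".
- SAP Section 3, Table 2 defines the PK analysis set as "All randomly assigned participants who received at least 1 study intervention and have evaluable PK data", so a participant with one period can belong to it. It defines the completer set thus: "For each PK primary parameter, only include participants who received all study interventions, and have evaluable PK data for both treatment periods". tmax is not a primary parameter.
- SAP 4.3.1 lists tmax among the PK parameters and says "Actual sampling times will be used in the final analyses of individual PK parameters".
- SAP 4.7: "There are no changes from the protocol specified statistical analyses".

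**The concern.** A rank-sum test needs two independent groups. In a 2-period, 2-sequence crossover the devices are not independent groups, because each completing participant gives a tmax to both. The sequences are independent, so a rank-sum test of Period 1 minus Period 2 differences between sequences is valid. SAP 4.3.2 names sequence, period and subject for Cmax and AUC; SAP 4.4 names none of them for tmax.

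Someone taking SAP 4.1 as the full specification could rank tmax by device over everyone in the PK analysis set, including one-period participants who cannot contribute a difference. Two programmers could then print different p-values. The by-device version would lose power and could disagree with the CI beside it.

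**Working it through.** **1. The plan's own figure.** No sample size, power or significance level is stated for tmax. The only figure is at least 95% power for Cmax and AUC (SAP Section 5: 54 completers, CV 24%, ratio 1.05, limits 0.8 to 1.25). With σ_w = √ln(1 + 0.24²) = 0.2366, SE = 0.2366 × √(2/54) = 0.0455 and 52 df, exact two one-sided test power is 98.4% per parameter. The figure is met, and tmax does not enter it.

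**2. Does the SAP prescribe the by-device form?** SAP 4.1 fixes a population and an as-received label. The same sentence governs the primary model in SAP 4.3.2, which keeps treatment, sequence, period and subject within sequence. It therefore cannot by itself imply an unpaired test. Period differences can be formed within the PK analysis set from participants with tmax in both periods; the others drop out of the test because they have no difference. The by-device form is neither ruled out nor implied. The median of differences and a CI from a bioequivalence procedure both point to the crossover form.

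**3. What if it were run by device?** Let r be the within-participant rank correlation. The difference in mean rank between devices has variance proportional to (1 − r), while the rank-sum test assumes r = 0. A nominal two-sided 10% test (a level assumed here to match the 90% CI) then has true size 2Φ(−1.645/√(1 − r)):

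| r | 1.645/√(1 − r) | True size |
|---|---|---|
| 0 | 1.645 | 10.0% |
| 0.25 | 1.899 | 5.8% |
| 0.5 | 2.326 | 2.0% |
| 0.75 | 3.290 | 0.1% |

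For non-negative correlation the size never exceeds nominal.

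**4. Power, by simulation.** Assumptions, none from the documents: 27 participants per sequence, median tmax 24 h, log SD 0.5, a 0.2 log shift between devices, no period effect. tmax is placed on the scheduled sampling times (Day 36 taken as 840 h) with timing jitter of SD 0.05 h to represent actual times. Correlation here is on the log scale; log-scale values of 0.25 / 0.5 / 0.75 correspond to rank correlations of about 0.20 / 0.41 / 0.62, so the sizes differ from those in step 3.

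| Log-scale correlation | 0 | 0.25 | 0.5 | 0.75 |
|---|---|---|---|---|
| Size, by device | 10.1% | 6.4% | 3.3% | 0.9% |
| Size, period differences by sequence | 10.0% | 9.6% | 9.9% | 9.7% |
| Power, by device | 59% | 60% | 62% | 65% |
| Power, period differences by sequence | 59% | 68% | 81% | 95% |

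**5. Disagreement between p-value and CI.** This depends on the CI formula, which the documents do not show. Same scenarios, by-device p-value:

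| Assumed 90% CI | Outcome | 0 | 0.25 | 0.5 | 0.75 |
|---|---|---|---|---|---|
| Half the Hodges-Lehmann interval between sequences | p ≥ 0.10, CI excludes zero | 4.8% | 10.6% | 19.9% | 30.1% |
| | p < 0.10, CI includes zero | 5.7% | 2.9% | 0.9% | 0.1% |
| Order-statistic interval for the plain median of differences | p ≥ 0.10, CI excludes zero | 3.7% | 4.8% | 10.1% | 17.3% |
| | p < 0.10, CI includes zero | 22.7% | 17.2% | 10.7% | 4.9% |

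At correlation 0.5 the first kind of disagreement halves with the second interval, and the reverse kind rises from 0.9% to 10.7%. No single conflict rate can be attributed to this plan.

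**6. Time basis and direction.** Nominal times would create heavy ties, but SAP 4.3.1 already fixes actual times for PK parameters. SAP 4.3.2 sets MUPFP as test and SDP as reference, and SAP 4.4 names the devices in that order.

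**The case for a change.** The best case for acting is that the ambiguity is real and costs one sentence to remove. tmax is the only secondary PK endpoint, the test is named in both documents and defined in neither, and the completer set that would settle who enters is limited to primary parameters. Fixing the ranked quantity and the groups before data are seen removes an analyst choice, and at high correlation that choice matters: 65% against 95% power at log-scale correlation 0.75 under the assumptions above.

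The gap and the arithmetic stand. What does not follow is that the plan leads to a wrong result. No stated rule selects the by-device form, the valid form is compatible with every sentence in SAP 4.4, and the procedure cited for the CI may already settle the point, although its text is not in the documents. The power gap also matters little where nothing is decided by rejecting: tmax has no equivalence limit, and the p-value is presented in addition to the estimate and its CI. Tie handling and the exact interval formula are ordinary programming detail for such a result. Naming the test's inputs would not depart from the protocol, which names the same test, so the statement in SAP 4.7 holds as it is.

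**Conclusion.** No change to the plan is called for. SAP 4.4 and Protocol 9.3.3 leave out what the rank-sum test ranks, its groups and its participants. In a 2×2 crossover, beside a median of differences and a bioequivalence CI, the sensible reading is period differences compared between sequences in participants with tmax in both periods.

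The worst case is a conservative, less powerful descriptive p-value. Under the assumed inputs the power loss runs from nothing at zero correlation to about 30 percentage points at log-scale correlation 0.75. This rests on an assumed tmax spread, shift, correlation and 10% level, and on non-negative within-participant correlation. False positives are not inflated, the sample size is unaffected, and the Cmax and AUC bioequivalence conclusion does not use the test. The judgement would differ if a significance level, limit or claim were tied to the tmax p-value; none is.

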4.5. Safety Analyses

4.5.1. Extent of Exposure

Exposure data will be listed.

4.5.2. Adverse Events

A treatment-emergent AE is defined as an AE which occurs after the first dose of study intervention of period 1 or which is present prior to dosing and becomes more severe post first dose. All AEs will be listed. Treatment-emergent AEs will be summarized by treatment (MUPFP, SDP, and Overall) and severity. The frequency (the number of AEs, the number of subjects experiencing an AE and the percentage of subjects experiencing an AE) of treatment-emergent AEs will be summarized by treatment, Medical Dictionary for Regulatory Activities (MedDRA) system organ class and preferred term. Serious AEs will be listed.

Discontinuations due to AEs will be listed.

4.5.3. Device Product Complaints (if applicable)

Devices product complaints will be listed.

4.5.4. Hypoglycemic Events

Hypoglycemic events will be appropriately recorded in the CRF. Hypoglycemic events are defined as follows:

Table 3. Hypoglycemic events

Category	Glucose
Level 1 hypoglycemia	<70 mg/dL (3.9 mmol/L) and \geq 54 mg/dL (3.0 mmol/L)
Level 2 hypoglycemia	<54 mg/dL (3.0 mmol/L)
Level 3 (Severe) hypoglycemia	N/A
Nocturnal hypoglycemia	N/A

Severe hypoglycemia is a severe event characterized by altered mental and/or physical status requiring assistance for treatment of hypoglycemia. Details can be found in the protocol.

Nocturnal hypoglycemia is a hypoglycemic event (including severe event) that occurred at night and presumably during sleep –between bedtime and waking.

Hypoglycemic events will be listed.

4.5.5. Vital Signs

Vital signs data will be summarized by treatment together with changes from baseline, where baseline is defined as the Day 1 Predose assessment.

4.5.6. Electrocardiograms

ECGs will be performed for safety monitoring purposes only and will not be presented. Any clinically significant findings from ECGs will be reported as an AE.

4.5.7. Injection Site Reactions

Injection-site assessments for local tolerability will be conducted, when reported as:

- an AE from a subject, or
- a clinical observation from an investigator.

Injection site assessment data (erythema, induration, categorical pain, pruritus, and edema) will be listed and summarized by treatment in frequency tables.

4.5.8. Clinical Laboratory Parameters

Values for any clinical chemistry, hematology and urinalysis values outside the reference ranges will be listed.

4.6. Interim Analyses

No interim statistical analyses are planned.

4.7. Changes to Protocol-Planned Analyses

There are no changes from the protocol specified statistical analyses.

5. Sample Size Determination

Approximately 65 participants may be enrolled so that approximately 54 evaluable participants complete the study. A sample size of 54 participants will provide at least 95% power that the 90% confidence interval of the geometric mean ratio of C_{max} and AUC between the 2 devices will fall within the equivalence range of 0.8 to 1.25. This assumes a nominal expected mean ratio of 1.05 (test vs reference), a within-subject coefficient of variation of 24%.

6. Supporting Documentation

Not applicable.

7. References

Signature Page for VV-CLIN-075821 v1.0

Approval

PPD

08-Mar-2023 13:35:51 GMT+0000

Signature Page for VV-CLIN-075821 v1.0

Approved on 08 Mar 2023 GMT
